(1, 1, 1)	xx.xx% (xx/xx)	[xx.xx%, xx.xx%]
(1, 1, 0)	xx.xx% (xx/xx)	[xx.xx%, xx.xx%]
(1, 0, 1)	xx.xx% (xx/xx)	[xx.xx%, xx.xx%]
(0, 1, 1)	xx.xx% (xx/xx)	[xx.xx%, xx.xx%]
(1, 0, 0)	xx.xx% (xx/xx)	[xx.xx%, xx.xx%]
(0, 1, 0)	xx.xx% (xx/xx)	[xx.xx%, xx.xx%]
(0, 0, 1)	xx.xx% (xx/xx)	[xx.xx%, xx.xx%]
Branch % Diameter Stenosis		
Mean±SD (N)	xx.xx±xx.xx (xx)	[xx.xx, xx.xx]
Median (Q1, Q3)	xx.xx (xx.xx, xx.xx)	
Range (min, max)	(xx.xx, xx.xx)	

Data presented in this table is from the Angiographic Core Laboratory.

Table 9 Quantitative Angiographic Findings – Intention-to-Treat Analysis

Set

	ITT Subjects (N=xx subjects)	95% CI
Baseline		
Reference Vessel Diameter (mm)		
Mean±SD (N)	xx.xx±xx.xx (xx)	[xx.xx, xx.xx]
Median (Q1, Q3)	xx.xx (xx.xx, xx.xx)	
Range (min, max)	(xx.xx, xx.xx)	
MLD (mm)		
Mean±SD (N)	xx.xx±xx.xx (xx)	[xx.xx, xx.xx]
Median (Q1, Q3)	xx.xx (xx.xx, xx.xx)	
Range (min, max)	(xx.xx, xx.xx)	
% Diameter Stenosis		
Mean±SD (N)	xx.xx±xx.xx (xx)	[xx.xx, xx.xx]
Median (Q1, Q3)	xx.xx (xx.xx, xx.xx)	
Range (min, max)	(xx.xx, xx.xx)	
Final		
Reference Vessel Diameter (mm)		
Mean±SD (N)	xx.xx±xx.xx (xx)	[xx.xx, xx.xx]
Median (Q1, Q3)	xx.xx (xx.xx, xx.xx)	
Range (min, max)	(xx.xx, xx.xx)	
In-Segment MLD (mm)		
Mean±SD (N)	xx.xx±xx.xx (xx)	[xx.xx, xx.xx]
Median (Q1, Q3)	xx.xx (xx.xx, xx.xx)	
Range (min, max)	(xx.xx, xx.xx)	
In-Segment % Diameter Stenosis		
Mean±SD (N)	xx.xx±xx.xx (xx)	[xx.xx, xx.xx]
Median (Q1, Q3)	xx.xx (xx.xx, xx.xx)	
Range (min, max)	(xx.xx, xx.xx)	

In-Stent MLD (mm)		
Mean±SD (N)	xx.xx±xx.xx (xx)	[xx.xx, xx.xx]
Median (Q1, Q3)	xx.xx (xx.xx, xx.xx)	
Range (min, max)	(xx.xx, xx.xx)	
In-Stent % Diameter Stenosis		
Mean±SD (N)	xx.xx±xx.xx (xx)	[xx.xx, xx.xx]
Median (Q1, Q3)	xx.xx (xx.xx, xx.xx)	
Range (min, max)	(xx.xx, xx.xx)	
Prox Edge MLD (mm)		
Mean±SD (N)	xx.xx±xx.xx (xx)	[xx.xx, xx.xx]
Median (Q1, Q3)	xx.xx (xx.xx, xx.xx)	
Range (min, max)	(xx.xx, xx.xx)	
Prox Edge % Diameter Stenosis		
Mean±SD (N)	xx.xx±xx.xx (xx)	[xx.xx, xx.xx]
Median (Q1, Q3)	xx.xx (xx.xx, xx.xx)	
Range (min, max)	(xx.xx, xx.xx)	
Distal Edge MLD (mm)		
Mean±SD (N)	xx.xx±xx.xx (xx)	[xx.xx, xx.xx]
Median (Q1, Q3)	xx.xx (xx.xx, xx.xx)	
Range (min, max)	(xx.xx, xx.xx)	
Distal Edge % Diameter Stenosis		
Mean±SD (N)	xx.xx±xx.xx (xx)	[xx.xx, xx.xx]
Median (Q1, Q3)	xx.xx (xx.xx, xx.xx)	
Range (min, max)	(xx.xx, xx.xx)	

Data presented in this table is from the Angiographic Core Laboratory.

Table 10 Final Angiographic Findings – Intention-to-Treat Analysis Set

	ITT Subjects (N=xx subjects)	95% CI
Thrombus	xx.xx% (xx/xx)	[xx.xx%, xx.xx%]
Aneurysm	xx.xx% (xx/xx)	[xx.xx%, xx.xx%]
Final TIMI		
0	xx.xx% (xx/xx)	[xx.xx%, xx.xx%]
1	xx.xx% (xx/xx)	[xx.xx%, xx.xx%]
2	xx.xx% (xx/xx)	[xx.xx%, xx.xx%]
3	xx.xx% (xx/xx)	[xx.xx%, xx.xx%]
No Reflow	xx.xx% (xx/xx)	[xx.xx%, xx.xx%]
Abrupt Closure	xx.xx% (xx/xx)	[xx.xx%, xx.xx%]
Spasm	xx.xx% (xx/xx)	[xx.xx%, xx.xx%]
Dissection		
0	xx.xx% (xx/xx)	[xx.xx%, xx.xx%]
A	xx.xx% (xx/xx)	[xx.xx%, xx.xx%]
B	xx.xx% (xx/xx)	[xx.xx%, xx.xx%]
C	xx.xx% (xx/xx)	[xx.xx%, xx.xx%]
D	xx.xx% (xx/xx)	[xx.xx%, xx.xx%]
E	xx.xx% (xx/xx)	[xx.xx%, xx.xx%]
F	xx.xx% (xx/xx)	[xx.xx%, xx.xx%]
Staining	xx.xx% (xx/xx)	[xx.xx%, xx.xx%]
Distal Embolism	xx.xx% (xx/xx)	[xx.xx%, xx.xx%]
Perforation	xx.xx% (xx/xx)	[xx.xx%, xx.xx%]
Branch % Diameter Stenosis		
Mean±SD (N)	xx.xx±xx.xx (xx)	[xx.xx, xx.xx]
Median (Q1, Q3)	xx.xx (xx.xx, xx.xx)	
Range (min, max)	(xx.xx, xx.xx)	

Data presented in this table is from the Angiographic Core Laboratory.

**Table 11a Combined In and Out-of-Hospital Complications to xx days–
Intention-to-Treat Analysis Set**

	ITT Subjects (N=xx subjects)	95% CI
To 30-day		
TVF (Cardiac death, Target Vessel MI, and Clinically-driven TVR)	xx.xx% (xx/xx)	[xx.xx%, xx.xx%]
Death	xx.xx% (xx/xx)	[xx.xx%, xx.xx%]
Cardiac Death	xx.xx% (xx/xx)	[xx.xx%, xx.xx%]
Non-Cardiac Death	xx.xx% (xx/xx)	[xx.xx%, xx.xx%]
All Cause MI (ARC)	xx.xx% (xx/xx)	[xx.xx%, xx.xx%]
Peri-Procedural PCI		
Peri-Procedural CABG	xx.xx% (xx/xx)	[xx.xx%, xx.xx%]
Spontaneous	xx.xx% (xx/xx)	[xx.xx%, xx.xx%]
Silent	xx.xx% (xx/xx)	[xx.xx%, xx.xx%]
Sudden Death	xx.xx% (xx/xx)	[xx.xx%, xx.xx%]
Reinfarction	xx.xx% (xx/xx)	[xx.xx%, xx.xx%]
Q wave MI	xx.xx% (xx/xx)	[xx.xx%, xx.xx%]
Non-Q wave MI	xx.xx% (xx/xx)	[xx.xx%, xx.xx%]
Target Vessel MI	xx.xx% (xx/xx)	[xx.xx%, xx.xx%]
Target Vessel Q wave MI	xx.xx% (xx/xx)	[xx.xx%, xx.xx%]
Target Vessel Non-Q wave MI	xx.xx% (xx/xx)	[xx.xx%, xx.xx%]
Non-Target Vessel MI	xx.xx% (xx/xx)	[xx.xx%, xx.xx%]
Non-Target Vessel Q wave MI	xx.xx% (xx/xx)	[xx.xx%, xx.xx%]
Non-Target Vessel Non-Q wave MI	xx.xx% (xx/xx)	[xx.xx%, xx.xx%]
All Revascularization	xx.xx% (xx/xx)	[xx.xx%, xx.xx%]
PCI	xx.xx% (xx/xx)	[xx.xx%, xx.xx%]
CABG	xx.xx% (xx/xx)	[xx.xx%, xx.xx%]
Clinically-driven Revascularization	xx.xx% (xx/xx)	[xx.xx%, xx.xx%]
PCI	xx.xx% (xx/xx)	[xx.xx%, xx.xx%]

CABG	xx.xx% (xx/xx)	[xx.xx%, xx.xx%]
Non-Clinically-driven Revascularization	xx.xx% (xx/xx)	[xx.xx%, xx.xx%]
PCI	xx.xx% (xx/xx)	[xx.xx%, xx.xx%]
CABG	xx.xx% (xx/xx)	[xx.xx%, xx.xx%]
All TLR	xx.xx% (xx/xx)	[xx.xx%, xx.xx%]
PCI	xx.xx% (xx/xx)	[xx.xx%, xx.xx%]
CABG	xx.xx% (xx/xx)	[xx.xx%, xx.xx%]
Clinically-driven TLR	xx.xx% (xx/xx)	[xx.xx%, xx.xx%]
PCI	xx.xx% (xx/xx)	[xx.xx%, xx.xx%]
CABG	xx.xx% (xx/xx)	[xx.xx%, xx.xx%]
Non-Clinically-driven TLR	xx.xx% (xx/xx)	[xx.xx%, xx.xx%]
PCI	xx.xx% (xx/xx)	[xx.xx%, xx.xx%]
CABG	xx.xx% (xx/xx)	[xx.xx%, xx.xx%]
All TVR	xx.xx% (xx/xx)	[xx.xx%, xx.xx%]
PCI	xx.xx% (xx/xx)	[xx.xx%, xx.xx%]
CABG	xx.xx% (xx/xx)	[xx.xx%, xx.xx%]
Clinically-driven TVR	xx.xx% (xx/xx)	[xx.xx%, xx.xx%]
PCI	xx.xx% (xx/xx)	[xx.xx%, xx.xx%]
CABG	xx.xx% (xx/xx)	[xx.xx%, xx.xx%]
Non-Clinically-driven TVR	xx.xx% (xx/xx)	[xx.xx%, xx.xx%]
PCI	xx.xx% (xx/xx)	[xx.xx%, xx.xx%]
CABG	xx.xx% (xx/xx)	[xx.xx%, xx.xx%]
All Non-TVR	xx.xx% (xx/xx)	[xx.xx%, xx.xx%]
PCI	xx.xx% (xx/xx)	[xx.xx%, xx.xx%]
CABG	xx.xx% (xx/xx)	[xx.xx%, xx.xx%]
Stent Thrombosis	xx.xx% (xx/xx)	[xx.xx%, xx.xx%]
Acute (0-24 hours)	xx.xx% (xx/xx)	[xx.xx%, xx.xx%]
Subacute (1-30 days)	xx.xx% (xx/xx)	[xx.xx%, xx.xx%]
Late (31 days-1 year)	xx.xx% (xx/xx)	[xx.xx%, xx.xx%]
To 9-month		
To 1-year		
To 2-year		

To 3-year

Denominators for 30-day events will reflect the number of patients with an adjudicated event in 30 days or follow-up through 16 days.

Denominators for 9-month events will reflect the number of patients with an adjudicated event in 270 days or follow-up through 240 days.

Denominators for 1-year events will reflect the number of patients with an adjudicated event in 365 days or follow-up through 335 days.

Denominators for 2-year events will reflect the number of patients with an adjudicated event in 730 days or follow-up through 700 days.

Denominators for 3-year events will reflect the number of patients with an adjudicated event in 1095 days or follow-up through 1065 days.

**Table 11b Combined In and Out-of-Hospital Complications to xx days-
Per-Protocol Analysis Set**

Table 12 Adverse Events – Intention-to-Treat Analysis Set

Adverse Events	Number of Events	ITT Subjects (N=xx subjects)
Any Adverse Event	xx	xx.xx% (xx/xx)
System Organ Class Term	xx	xx.xx% (xx/xx)
Preferred Term	xx	xx.xx% (xx/xx)

Table 13 Serious Adverse Events – Intention-to-Treat Analysis Set

Serious Adverse Events	Number of Events	ITT Subjects (N=xx subjects)
Any Serious Adverse Event	xx	xx.xx% (xx/xx)
System Organ Class Term	xx	xx.xx% (xx/xx)
Preferred Term	xx	xx.xx% (xx/xx)

Table 14 Device Malfunction, Failure or Misuse Issues – Intention-to-Treat Analysis Set

Device malfunction, failure, or misuse issue	Device-based (D=xx devices)	Subject-based (N=xx subjects)
Unable to cross lesion with device and removed	xx	xx.xx% (xx/xx)
Stent detachment	xx	xx.xx% (xx/xx)
Failure to deploy device	xx	xx.xx% (xx/xx)
Inability to retrieve catheter	xx	xx.xx% (xx/xx)
Dislodgement of device	xx	xx.xx% (xx/xx)
Device deployed at unintended site	xx	xx.xx% (xx/xx)
Balloon burst	xx	xx.xx% (xx/xx)
Other balloon failure	xx	xx.xx% (xx/xx)
Device opened but not used	xx	xx.xx% (xx/xx)
Physician decision not to use the study device	xx	xx.xx% (xx/xx)
Device explanted or removed	xx	xx.xx% (xx/xx)
Inadequate labeling	xx	xx.xx% (xx/xx)
Other	xx	xx.xx% (xx/xx)

Table 15 Protocol Deviation by Type – Intention-to-Treat Analysis Set

Protocol Deviations	ITT Subjects (N=xx subjects)
Informed Consent Violation	
Not obtained prior to study screening	xx.xx% (xx/xx)
Wrong version used	xx.xx% (xx/xx)
Expired version used	xx.xx% (xx/xx)
Not dated	xx.xx% (xx/xx)
Not signed	xx.xx% (xx/xx)
General Inclusion Criteria Violation	
Angiographic Inclusion Criteria Violation	xx.xx% (xx/xx)
General Exclusion Criteria Violation	
Angiographic Exclusion Criteria Violation	xx.xx% (xx/xx)
Follow-up Compliance Violation	
30-day visit out of window	xx.xx% (xx/xx)
30-day visit data obtained by medical records only	xx.xx% (xx/xx)
30-day visit not done	xx.xx% (xx/xx)
1-year visit out of window	xx.xx% (xx/xx)
1-year visit data obtained by medical records only	xx.xx% (xx/xx)
1-year visit not done	xx.xx% (xx/xx)
2-year visit out of window	xx.xx% (xx/xx)
2-year visit data obtained by medical records only	xx.xx% (xx/xx)
2-year visit not done	xx.xx% (xx/xx)
3-year visit out of window	xx.xx% (xx/xx)
3-year visit data obtained by medical records only	xx.xx% (xx/xx)
3-year visit not done	xx.xx% (xx/xx)
Lab Value Violation	
Pregnancy test (female subjects) not done	xx.xx% (xx/xx)
CBC not done	xx.xx% (xx/xx)
Chemistry not done	xx.xx% (xx/xx)
INR not done	xx.xx% (xx/xx)

aPTT not done	xx.xx% (xx/xx)
Baseline CK not done	xx.xx% (xx/xx)
Baseline CK-MB not done	xx.xx% (xx/xx)
Baseline troponin not done	xx.xx% (xx/xx)
Serial CK not done	xx.xx% (xx/xx)
Serial CK-MB not done	xx.xx% (xx/xx)

Clinical Assessment Violation

Baseline 12-lead ECG not done	xx.xx% (xx/xx)
Baseline 12-lead ECG done out of window	xx.xx% (xx/xx)
Baseline ECG not 12-lead	xx.xx% (xx/xx)
Baseline ECG data not available	xx.xx% (xx/xx)
Baseline physical exam not done	xx.xx% (xx/xx)
Discharge physical exam not done	xx.xx% (xx/xx)
Procedural Angiography not done	xx.xx% (xx/xx)

Procedural Assessments Violation

Pre-dilation not performed	xx.xx% (xx/xx)
Inappropriate size stent used	xx.xx% (xx/xx)
Inappropriate size balloon used for pre-dilatation	xx.xx% (xx/xx)
Unacceptable other therapies used	xx.xx% (xx/xx)
Treatment of target lesion not attempted	xx.xx% (xx/xx)
Target lesion not treated with NIRxcell	xx.xx% (xx/xx)
Target lesion treated not native/ de novo lesion	xx.xx% (xx/xx)
Treatment of an additional lesion	xx.xx% (xx/xx)

Medication Violation

Information regarding relevant medication not collected	xx.xx% (xx/xx)
Pre-procedure ASA dose not per protocol	xx.xx% (xx/xx)
ASA temporarily interrupted	xx.xx% (xx/xx)
ASA discontinued prior to study completion	xx.xx% (xx/xx)
ASA not taken at all	xx.xx% (xx/xx)
Pre-procedure Thienopyridine dose not per protocol	xx.xx% (xx/xx)
Thienopyridine temporarily interrupted prior to 1-month follow-up	xx.xx% (xx/xx)
Thienopyridine discontinued prior to 1-month follow-up	xx.xx% (xx/xx)

Thienopyridine not taken at all	xx.xx% (xx/xx)
Heparin/Bivalirudin not given per protocol	xx.xx% (xx/xx)
Nitroglycerin not given per protocol	xx.xx% (xx/xx)
Serious Adverse Event not reported within the Protocol required time frame	xx.xx% (xx/xx)
Other	xx.xx% (xx/xx)

Listing 1 Patient-based Listing

Site	Patient	Demographic Characteristics	Medical Historic Characteristics	Acute Success
xxx	Xxx	Refer to Table 5	Refer to Table 5	Refer to Table 1.2

[figure not shown]
Listing 2 Lesion-based Listing

Site	Patient	Lesion Length	Eccentric	Thrombus	Calcification	Baseline RVD	Baseline MLD	Baseline % DS	Final RVD	Final In-Segment MLD	Final In-Segment % DS	Final In-Stent MLD	Final In-Stent % DS
XXX	XXX												

Listing 3 Device Malfunction, Failure or Misuse Issues

[figure not shown]
Site	Patient	Stent Type	Stent location to lesion	Device malfunction, failure, or misuse issue
XXX	XXX	XXX	XXX	Refer to Table 14

Figure 1 Flow Chart – Intention-to-Treat Analysis Set

**Figure 2 Kaplan-Meier Survival from TVF from Procedure to xx Days –
Intent- to-Treat Analysis Set**

TVF	Time after Procedure (days)						
	0	1-180	181-360	361-540	541-720	721-900	901-1080

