## 7.2 Procedural Information

For information describing the procedural steps and materials necessary for appropriate use of the NIRxcell Stent System, refer to the US Instructions for Use.

Additionally, note the following:

- *Start of the Procedure and Enrollment*

The start of the procedure is defined as the time of arterial cannulation. Actual enrollment in the study occurs at the time the study device is introduced into the body. If the angiogram performed at the index procedure indicates that the subject is not a candidate for the study, this subject is not considered enrolled.

- *Angiographic Protocol Requirement*

- Following intracoronary injection of 50–200 µg nitroglycerin (NTG), obtain baseline angiograms using at least  $\geq 2$  near orthogonal views, best demonstrating the coronary artery stenosis, as specified in the angiographic protocol.
- Before stent placement, obtain a single working view of the coronary artery stenosis, as specified in the angiographic protocol.

- *Pre-Dilatation*

If the target lesion fulfills eligibility criteria, the target lesion must be pre-treated with standard percutaneous transluminal balloon angioplasty. This clinical protocol does not allow for direct stenting of the target vessel.

Attention must be paid to the pre-dilatation technique to avoid balloon injury to any segment of the vessel that will not be entirely covered by the stent ('geographical miss').

Pre-dilatation must be performed using a balloon with the following 3 characteristics:

1. A diameter  $\geq 0.5$  mm smaller than the treatment stent.
2. A length matching or shorter than the lesion length to be dilated (to avoid dilatation of the vessel wall adjacent to the stent).
3. A length shorter than the stent to be implanted.

The use of other therapy (e.g. cutting balloons, atherectomy, laser, thrombectomy, etc.) is not allowed.

- *Selection of Appropriately Sized Stent*

Select an appropriately sized stent based on angiographic vessel measurements (approximately 2–4 mm longer than the measured shoulder-to-shoulder lesion length, with a stent to distal reference vessel ratio of 1:1 or 1.1:1.0). The intention should be to cover the whole lesion with 1 stent of adequate length.

**Note:** Additional NIRxcell Stent Systems should be used, at the physician's discretion, for sub-optimal result, or in the event of bailout procedures, as defined below.

- *Bailout Procedures*

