The intention should be to cover the index lesion with 1 stent of adequate length. Bailout procedures and additional stenting for sub-optimal results should be avoided unless required for subject safety. If a subject enrolled in the study experiences a major dissection or an occlusive complication (as evidenced by decreased target vessel flow, chest pain, or ischemic ECG changes that do not respond to repeat balloon inflations, NTG, intracoronary verapamil, intracoronary diltiazem, or lytic agents), bailout procedures may be performed. For bailout procedures or in the event of a sub-optimal result, further stenting may be employed, at investigator's discretion, using the NIRxcell Stent Systems, as required.

- *End of the Procedure*

The end of the procedure is defined as the time that the final guiding catheter is withdrawn from the subject. Closure of the arterial puncture site will be performed as per laboratory

standards. The hemostasis introducer sheath(s) may be removed when the subject's activated clotting time (ACT) is <150 seconds or per the physician's discretion. If a guide catheter is introduced once the procedure is considered over, as defined above, or the subject is returned to the procedure room and interventional therapy is performed, this should be considered a repeat intervention.

- *Adverse Events Recording*

All adverse events (AEs) occurring following informed consent signature must be recorded.

**Note:** Bailout procedures performed during the same catheterization as the index stenting procedure shall be considered part of the index procedure.

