### **Detailed Explanations**

**Adverse Events:** Adverse events occurring (1) from time of index procedure to 30 days follow-up contact, (2) From 30 days follow up contact to 1 year follow-up contact, (3) From 1 year follow-up contact to 2 years follow-up contact, and (4) From 2 years follow-up contact to 3 years follow-up contact, will be recorded. In the event of an AE that is associated with repeat

angiography/revascularization, the event related coronary angiograms and catheterization report must be captured and submitted to the data center within 10 working days of knowledge of the event. Angiographic data collected during any repeat procedure on the target vessel must be made available to the CEC for an independent review and assessment. Likewise, the angiographic images should be submitted to the core laboratory for an independent review and assessment of the target lesion and study stent.

**12-Lead ECG:** According to each site's standard of care.

**CBC With Differential:** Hematology testing due to anti-platelet therapy should follow the routine standard of care.

**CK, CK-MB and Troponin:** CK, CK-MB or troponin will be obtained pre-procedure (within 24 hours of the index procedure). Post procedure, CK and CK-MB will be measured at 6- 8 hours, 12-16 hours and 20-24 hours post procedure (or upon discharge, whichever comes first). If any CK elevation (CK above ULN) is noted post procedure, CK and CK-MB measurements will continue to be performed every 8 hours for 24 hours starting from when the first elevation is noted and recorded on the appropriate eCRF. If total CK values are within normal ranges, CK-MB measurements may not be performed (per hospital standards). However, it is strongly encouraged that CK-MB measurements are obtained with every total CK drawn, even if CK values are within normal limits. It is also recommended that sites collect CK and CK-MB preferentially over troponin in the peri-procedural period subsequent to the index procedure. In the case where CK and CK-MB are not available, troponin can be used.

**Relevant Medications:** Statins, ACE-I, ARB, beta-blockers and anti-platelets.

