### 11.1 Definition of Adverse Event and Serious Adverse Event

#### 11.1.1 Adverse Event

An AE is defined as any untoward medical occurrence, unintended disease or injury, or untoward clinical signs (including abnormal laboratory findings) in subjects, users or other persons, whether or not related to the study device.

**NOTE 1:** This definition includes events related to the study device or the comparator.

**NOTE 2:** This definition includes events related to the procedures involved.

**NOTE 3:** For users or other persons, this definition is restricted to events related to the study device.

In this study, AEs shall be assessed and documented at IC signing. All AEs are to be recorded through the end of the study on the appropriate subject case report forms and followed through to their resolution regardless of time window.

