**11.3 Documentation**

AEs must be listed on the appropriate eCRF.

All AEs will be characterized by the following criteria:

- Intensity or Severity
- Relatedness
- Outcome
- Treatment or Action Taken

All AEs (serious and non-serious) will be reported for the entire study period in accordance with national laws.

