4.4 Adverse Events

A Treatment Emergent Adverse Event (TEAE) is an event that emerges, or a pre-existing event that worsens, any time during or after stent implantation. Adverse events will be coded by the MedDRA system version 18.1 or later. The per-event and per-patient incidence of TEAEs will be presented overall and by MedDRA system organ class and preferred term. This will be repeated for serious TEAEs.

5 TABLES, FIGURES, and LISTINGS

Table 1.1a Primary Endpoints – Intention-to-Treat Analysis Set

Primary Endpoint	ITT Subjects with Available Data (N=xx subjects)	Two-sided Binomial Exact 95% CI
TVF at 3 years	xx.xx% (xx/xx)	[xx.xx%, xx.xx%]
Cardiac Death	xx.xx% (xx/xx)	[xx.xx%, xx.xx%]
Target Vessel MI	xx.xx% (xx/xx)	[xx.xx%, xx.xx%]
Clinically-driven TVR	xx.xx% (xx/xx)	[xx.xx%, xx.xx%]

Note: Events defined for the period of 3 year post-procedure follow up are reported for patients with at least 1050 days of follow-up or with event to 3 years (1080 days).

Table 1.1b Primary Endpoints – Per-Protocol Analysis Set

Table 1.2 Secondary Endpoints – Intention-to-Treat Analysis Set

	ITT Subjects (N=xx subjects)	Two-sided Binomial Exact 95% CI
TVF at 9 months	xx.xx% (xx/xx)	[xx.xx%, xx.xx%]
All Cause Death		
30-day	xx.xx% (xx/xx)	[xx.xx%, xx.xx%]
1-year	xx.xx% (xx/xx)	[xx.xx%, xx.xx%]
2-year	xx.xx% (xx/xx)	[xx.xx%, xx.xx%]
3-year	xx.xx% (xx/xx)	[xx.xx%, xx.xx%]
Cardiac Death		
30-day	xx.xx% (xx/xx)	[xx.xx%, xx.xx%]
1-year	xx.xx% (xx/xx)	[xx.xx%, xx.xx%]
2-year	xx.xx% (xx/xx)	[xx.xx%, xx.xx%]
3-year	xx.xx% (xx/xx)	[xx.xx%, xx.xx%]
All Cause MI		
30-day	xx.xx% (xx/xx)	[xx.xx%, xx.xx%]
1-year	xx.xx% (xx/xx)	[xx.xx%, xx.xx%]
2-year	xx.xx% (xx/xx)	[xx.xx%, xx.xx%]
3-year	xx.xx% (xx/xx)	[xx.xx%, xx.xx%]
Target Vessel MI		
30-day	xx.xx% (xx/xx)	[xx.xx%, xx.xx%]
1-year	xx.xx% (xx/xx)	[xx.xx%, xx.xx%]
2-year	xx.xx% (xx/xx)	[xx.xx%, xx.xx%]
3-year	xx.xx% (xx/xx)	[xx.xx%, xx.xx%]
Clinically-driven TLR		
30-day	xx.xx% (xx/xx)	[xx.xx%, xx.xx%]
1-year	xx.xx% (xx/xx)	[xx.xx%, xx.xx%]
2-year	xx.xx% (xx/xx)	[xx.xx%, xx.xx%]
3-year	xx.xx% (xx/xx)	[xx.xx%, xx.xx%]
Clinically-driven TVR		
30-day	xx.xx% (xx/xx)	[xx.xx%, xx.xx%]

1-year	xx.xx% (xx/xx)	[xx.xx%, xx.xx%]
2-year	xx.xx% (xx/xx)	[xx.xx%, xx.xx%]
3-year	xx.xx% (xx/xx)	[xx.xx%, xx.xx%]
Device Success ¹	xx.xx% (xx/xx)	[xx.xx%, xx.xx%]
Lesion Success ²	xx.xx% (xx/xx)	[xx.xx%, xx.xx%]
Procedure Success ³	xx.xx% (xx/xx)	[xx.xx%, xx.xx%]
Stent Thrombosis		
Discharge	xx.xx% (xx/xx)	[xx.xx%, xx.xx%]

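### Does starting the adverse-event summaries at stent implantation drop procedural events from the safety tables?

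*SAP*

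**What the plan says.** SAP 4.4 defines the treatment-emergent adverse event (TEAE): it "is an event that emerges, or a pre-existing event that worsens, any time during or after stent implantation". The section then presents TEAEs, and separately serious TEAEs, per event and per patient, by system organ class and preferred term. Tables 12 and 13 hold these summaries for the intention-to-treat set. Their shells refer to any adverse event and any serious adverse event and do not repeat the TEAE limit.

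Protocol 7.2 gives the time points that matter here. For the procedure it states: "The start of the procedure is defined as the time of arterial cannulation". For entry into the study, which comes later, it states: "Actual enrollment in the study occurs at the time the study device is introduced into the body". Before the stent is placed, "the target lesion must be pre-treated with standard percutaneous transluminal balloon angioplasty".

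On collection and scope:
- Protocol 7.2: "All adverse events (AEs) occurring following informed consent signature must be recorded".
- Protocol 9, Detailed Explanations: the first adverse-event interval runs "from time of index procedure to 30 days follow-up contact".
- Protocol 11.1.1, Note 2: "This definition includes events related to the procedures involved".
- Protocol 11.3: "All AEs (serious and non-serious) will be reported for the entire study period".

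**The concern.** The SAP's start point matches none of the time points that the protocol defines. The only time zero linked to implantation is in the stent thrombosis definition of Appendix 1-P. It falls after the subject has left the laboratory, which does not fit a window that includes events during implantation.

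Taken literally, implantation could mean the moment of deployment. Cannulation, contrast injection and the mandatory pre-dilatation all come earlier. A contrast or drug reaction at that stage that resolved without worsening would then fall outside the window. Such a reaction has no row in the endpoint, angiographic or device tables, and none of the three named listings is an adverse-event listing. A serious event of this kind could be missing from Table 13. An enrolled subject in whom no stent was deployed would have no start at all. Two programmers could also reach different counts from the same data.

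**Working it through.** No sample size, power or error rate is involved. The check compares the possible readings with the rest of the plan and then scales the effect.

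**1. Three readings of the start**

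| Reading | Procedural events left out | Does every enrolled subject have a start? |
|---|---|---|
| Deployment of the stent | Those from access, angiography, pre-dilatation and delivery, unless they later worsen | No, if no stent is deployed |
| Entry of the stent system into the body | Those from access, angiography and pre-dilatation, unless they later worsen | Yes, because this is the moment of enrollment (Protocol 7.2, SAP 2.2.4) |
| Index stenting procedure, from cannulation | None | Yes |

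Events at sheath removal or puncture closure follow stenting and are counted on every reading.

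**2. Which reading fits the rest of the plan**

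- SAP Table 1 and Protocol Table 2 place the first adverse-event record in the Procedure column.
- Protocol 9 starts the first adverse-event interval at the index procedure.
- Protocol 11.1.1 counts events related to the procedures involved.
- SAP 2.2 names the whole intervention the index stenting procedure and measures follow-up from it.
- SAP 2.2.4 and 4.2.1 keep every enrolled subject in the analysis whatever treatment followed. Deployment as the start is hard to square with this.

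The first four favour the index procedure. The last rules against deployment, the only reading that leaves a subject without a start.

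**3. Does the plan foresee a subject with no stent?**

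Table 6 has a row for failed delivery or a misplaced stent, and Table 14 one for a device that could not cross the lesion. Both describe what happened to a device. Another stent may follow, so these rows do not establish a subject with none. Such a subject remains conceivable, but has a start on two of the three readings.

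**4. Can the data separate the readings?**

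The readings differ only within a single catheterization. To apply a narrow one, a programmer needs the clock time of onset. The documents do not show that this is collected for adverse events. The onset item they name is a date, for unanticipated device effects (Protocol 11.4.2). The SAP counts its windows in days (4.3.3 and the footnotes to Tables 1.2 and 3). If onset is held by date, an event on the procedure day cannot be placed before or after deployment. Counting from the procedure date then includes it.

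**5. Scale if a narrow reading were applied**

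Input: N = 65 (SAP 2.2.2). If m subjects have an event of a given preferred term left out, and no other counted event of that term, the term's rate falls by 100 × m/65 percentage points:
- m = 1: 100 × 1/65 = 1.54
- m = 2: 100 × 2/65 = 3.08
- m = 3: 100 × 3/65 = 4.62

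The values of m are illustrative. The documents give no rate of events before implantation, and m may be 0. The any-event rate would move only for a subject with no other counted adverse event in three years.

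**The case for a change.** The best case for an edit is that it is cheap. One sentence could tie the start to the index procedure for all enrolled subjects, and two table titles could say that they show TEAEs. The start is undefined, the named listings include none for adverse events, and the text and shells of Tables 12 and 13 do not match on the TEAE limit.

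Those observations are accurate, but they carry less weight than they seem to. SAP 4.3 promises individual data in subject listings, although it names no adverse-event listing. The unlabelled shells do not themselves exclude any event. Flagging events that begin before device entry would need onset times that the documents do not show are collected.

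The choice of cannulation is also partly a preference. Cannulation precedes enrollment, and a subject found ineligible on the index angiogram is never enrolled. A cannulation start therefore counts pre-enrollment events only in those who went on to enrol. Device entry avoids this and gives every enrolled subject a start, at the cost of the earlier procedural events. What stands is that a clarifying phrase would do no harm.

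**Conclusion.** No change is needed. SAP 4.4 leaves a definition loose, and the surrounding text lets an analyst fill it sensibly by counting adverse events from the day of the index procedure for every enrolled subject, stent or no stent. Done that way, Tables 12 and 13 lose no procedural event.

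This rests on two assumptions: that the analyst reads SAP 4.4 together with the schedule and the protocol's adverse-event interval, and that onset is handled by date. If clock times were held and deployment used as the start, each affected subject would lower one term's rate by 1.5 points, and the number affected may be zero. All analyses are descriptive (SAP 4), and Tables 1.1, 1.2, 10, 11 and 14 do not depend on the TEAE start, so no endpoint result would change. Stating the start explicitly and labelling the two tables is an optional clarification.
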